### **Research Objectives**

**Objective 1. Investigate smokers' and providers' attitudes, knowledge, and experiences with the expanded 2021 USPSTF Lung Cancer Screening (LCS) recommendations.** We will examine it using exploratory sequential mixed methods (integrating quantitative and Qualitative data). We will conduct focus groups for A.A. smokers who are eligible for LDC. Results will be used to expand the understanding of the needs and barriers of LDCT LCS and smoking cessation services to construct multiple levels intervention with the goal of increasing LDCT uptake and quitting behaviors.

**Objective 2. Compare the Effectiveness of a Multiple levels intervention integrating lung cancer screening and smoking cessation (MILS) vs. control group on the biochemically validated 7-day point-prevalence tobacco abstinence rates at 6 months, LDCT uptake, the change in tobacco consumption pattern, nicotine dependence and stage of change was assessed.** We will conduct a multiple level intervention integrating lung cancer screening and smoking cessation (MILS), including individual level: individual-based LDCT/smoking education (with Louisiana Tobacco Cessation Initiative); Institutional level: provider education (with university medical center); and community level: a community navigator (Community Health Worker) with interactive social media to increase LDCT uptake and quitting behaviors in racially and ethnically diverse populations. Multilevel intervention is a holistic approach to addressing health issues that recognize the complexity of health determinants. Multilevel interventions aim to change health behaviors and related outcomes by targeting multiple levels of influence, such as individuals, groups, organizations, and communities. Multilevel interventions can be delivered simultaneously or over time to achieve desired outcomes. For example, interventions integrating lung cancer screening and smoking cessation can work together synergistically to enhance early cancer detection and prevention.

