LDCT is an evidence-supported lung cancer screening that is noted to increase early-stage lung cancer diagnosis. Early diagnosis can reduce lung cancer-related mortality and improve prognosis. **For this study, we are not directly providing lung cancer screenings. We are recruiting participants who are eligible for lung cancer screening and increase their knowledge, attitude, and intention to take LDCT.** We hypothesize that A.A. in the MILS group will achieve greater increases in LDCT uptake and quitting behaviors (e.g., biochemically validated 7-day point-prevalence tobacco abstinence rates at 6 months, the change in tobacco consumption pattern, nicotine dependence and stage of change) at post-treatment and follow-up than A.A. in the control group.

**Objective 3. Explore barriers and facilitators that influence primary outcomes at the community, provider, and individual levels for the improvement of a multilevel intervention (MILS).** We will conduct 30 qualitative key informant interviews (10 for each level) to identify barriers and facilitators that influence the adherence and implementation of MILS.

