### **Study Sample/Recruitment**

Participants of the study will be recruited from the University Medical Center (UMC). Eligibility criteria will include: (1) self-identified as African American; (2) eligible for a LDCT (i.e., 50-77 years old; 20+ pack years of smoking) or have received a LDCT exam in the past; (3) current

smoker; and (4) English speaking. Eligible participants will be recruited from Tobacco Control Initiative (TCI) staff at UMC. Objective 1: Based on our previous qualitative studies, we anticipate reaching saturation after 30 in-depth interviews; however, we will consider increasing the number of interviews if needed. Objective 2: Two hundred fifty eligible A.A. smokers at UMC will be identified and recruited by TCI staff or UMC clinic and referred/enrolled to evaluate the Effectiveness of a Multiple levels intervention integrating lung cancer screening and smoking cessation (MILS) utilize a two-arm, parallel groups, randomized, controlled design. Objective 3: Ten participants, 10 providers and 10 community members will be asked to complete an in-depth interview.

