### **Study Questionnaires/ Assessment Tools**

Primary outcomes were measured by survey before intervention, immediately after intervention, and 6-month after intervention. Outcomes include stage of change, 7-day PPA rate, 24-hour PPA rate, daily cigarette use, and the Fagerstrom Test for Nicotine Dependence score. Stage of Change was measured based on the TTM model. 7-day PPA at follow-up was measured with the question "Have you smoked any tobacco products in the last 7 days?" 24-hour PPA was measured using the question "Have you smoked any tobacco products in the last 24 hours?" Daily cigarette use was measured using a multiple-choice question with 4 answers: 1) 10 or less, 2) 11-20; 3) 21-30; or 4) 31 or more. The Fagerstrom Test for Nicotine Dependence was based on a 6-item validated questionnaire (Etter et al., 1999) Second, the LDCT uptake and intent to LCS constructs were measured by previously validated questionnaires. An additional amendment will be submitted for Year 2 measurements and aims. All surveys and questionnaires will be submitted in an amendment for Year 2 of the study, including all intervention materials.

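### Daily cigarette use is recorded in four bands whose lowest runs from 0 to 10, so the consumption-change outcome cannot register reduction among participants who start at 10 a day or fewer

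*Protocol*

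**What the plan says.** Under Research Objectives, Objective 2 compares MILS with control on several outcomes, including "the change in tobacco consumption pattern, nicotine dependence and stage of change was assessed". The hypothesis paragraph that follows predicts a greater improvement under MILS on the same measures.

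Under Study Questionnaires/ Assessment Tools, the outcomes are "measured by survey before intervention, immediately after intervention, and 6-month after intervention". The list reads: "Outcomes include stage of change, 7-day PPA rate, 24-hour PPA rate, daily cigarette use, and the Fagerstrom Test for Nicotine Dependence score". The daily-use item is fixed as follows: "Daily cigarette use was measured using a multiple-choice question with 4 answers: 1) 10 or less, 2) 11-20; 3) 21-30", with a fourth answer for 31 or more. No numeric count of cigarettes is described anywhere in the protocol. Abstinence is asked separately, over 7 days ("Have you smoked any tobacco products in the last 7 days") and over 24 hours. The same section says the questionnaires will be filed in an amendment for Year 2.

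Under Study Sample/Recruitment, entry requires a current smoker aged 50-77 with "20+ pack years of smoking", or someone who has had an LDCT before. No minimum daily consumption is set.

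**The concern.** A consumption outcome adds to an abstinence outcome by showing whether people who still smoke are smoking less. The banded item is weakest at exactly that. Its lowest band has a floor: everyone who starts in it stays in it, whatever they do, unless they increase. The bands above are about ten cigarettes wide, so sizeable reductions inside a band also disappear, while a cut of one cigarette across a boundary counts as an improvement.

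At stake is a named, directional comparison between arms. If MILS helps people cut down without quitting, this item may show little or nothing, and a null result would be hard to interpret. No later analysis plan can repair this, because a count that was never collected cannot be recovered from a band.

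**Working it through.** The protocol gives no power or effect size for this outcome, so there is no planned figure to reproduce. The powers in Data Analysis (85.6-99.6% for abstinence, 76.5-97.2% for LDCT uptake) concern other items.

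**1. Score the bands.** Let band = 1 for 0-10, 2 for 11-20, 3 for 21-30 and 4 for 31 or more, and change = follow-up band minus baseline band.

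| Cigarettes/day, baseline to follow-up | Bands | Change |
|---|---|---|
| 10 to 5 | 1 to 1 | 0 |
| 10 to 1 | 1 to 1 | 0 |
| 10 to 0 | 1 to 1 | 0 |
| 8 to 0 | 1 to 1 | 0 |
| 20 to 11 | 2 to 2 | 0 |
| 30 to 21 | 3 to 3 | 0 |
| 20 to 10 | 2 to 1 | -1 |
| 20 to 0 | 2 to 1 | -1 |
| 11 to 10 | 2 to 1 | -1 |

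Halving from 20 and quitting from 20 score alike. A cut of nine (20 to 11) scores 0, and a cut of one (11 to 10) scores -1.

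**2. Can light daily smokers enrol?** Pack-years = (cigarettes per day / 20) x years, taking 20 cigarettes to a pack. At 10 a day, 20 / (10/20) = 40 years reaches the threshold, which is feasible at ages 50-77. The past-LDCT route, as worded, does not restate a pack-year minimum. So they can enrol, but the protocol does not say how many will.

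**3. How much power is lost?** This needs assumptions that the protocol does not supply. The simulation used 2,000 trials per setting and 100 per arm (the number expected at 6 months in Data Analysis). Baseline use was lognormal with mean/SD of 10/6, 13/7 or 16/8 a day. Individual reduction had an SD of 25%, and quitters were set to 0. Follow-up was analysed with baseline as covariate, once on the number and once on the band, at two-sided 0.05. At mean 10 a day, 64% of participants start at 10 or fewer.

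| Scenario (MILS vs control) | Baseline mean | Power, number | Power, bands | Loss (points) |
|---|---|---|---|---|
| A. Reduction 20% vs 5%; quitting 5% in both | 10 | 79% | 52% | 27 |
| | 13 | 81% | 67% | 14 |
| | 16 | 83% | 75% | 8 |
| B. Reduction 5% in both; quitting 20% vs 5% | 10 | 61% | 16% | 45 |
| | 13 | 64% | 24% | 40 |
| | 16 | 65% | 33% | 32 |
| C. Reduction 20% vs 5%; quitting 20% vs 5% | 10 | 99% | 75% | 24 |
| | 13 | 99% | 91% | 8 |
| | 16 | 99% | 96% | 3 |

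The simulation standard error is at most sqrt(0.5 x 0.5 / 2000) = 0.011, about 1 point. The quit rates of 20% and 5% in B and C are the protocol's own low-end planning values. The number has more power than the bands as written in every row, and the gap shrinks as baseline use rises.

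**The case against.** The strongest reply is that the trial does not depend on this item. Quitting is recorded by the 7-day and 24-hour questions, and Objective 2 names biochemically validated abstinence at 6 months. The only powered outcomes are validated abstinence and LDCT uptake. All of this stands. It also limits the weight of scenario B, because a difference that arises only from quitting is tested directly by the abstinence outcome.

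A second reply is that a zero category can be built from the abstinence answers without a new item. In scenario C that raises the bands to 96-99% power, close to the number. This also stands, but only where extra quitting drives the effect. Under scenario A a derived zero does not repair the loss, because reduction within a band is still invisible.

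A third reply is that the baseline distributions are assumed. That is true. If few participants smoke 10 or fewer a day, the loss is small, and anyone who starts at 11 or more can move down a band.

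A reader might also infer that quitters have no answer to tick, leave the item blank, and so reduce the comparison to continuing smokers, a group selected after randomisation. The protocol does not support this. Zero is a valid reply under the lowest band, and no skip rule, blank or restriction to continuing smokers is described.

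A reader might likewise infer that a primary result is at risk, because the questionnaire section lists daily use in the paragraph that opens with primary outcomes. That paragraph lists five measures loosely, and the sample size rests on none of the banded data.

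**Conclusion.** The point holds for the consumption-change outcome and no further. That the item cannot show change within 0-10 a day, and that a participant who starts there cannot improve on it, follows from the answer options alone and needs no assumption.

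The size does rest on assumptions. With baseline means of 10 to 16 a day and 100 per arm, power falls from about 80% to 52-75% when the arms differ only in average reduction (20% vs 5%), and from 99% to 75-96% when quit rates also differ (20% vs 5%). The share of participants at 10 or fewer at baseline drives the result, and the protocol does not give it.

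The abstinence and LDCT conclusions are unaffected. This is a worthwhile measurement correction to a named secondary comparison, not a threat to the trial's main result.

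**What to change.** Before the Year 2 questionnaire amendment is filed, replace the four-answer item with a question asking for cigarettes per day as a whole number, zero allowed, at all three assessments and in both arms. Derive the four bands from the number wherever a score or table needs them; the reverse is impossible. Analyse the follow-up number with the baseline number as covariate.

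The cost is one survey item. The downside is digit preference: people tend to report round numbers such as 10 or 20. This assumes that no Objective 2 participant has yet completed the banded item at baseline, which fits the plan to submit the questionnaires in the Year 2 amendment. If some have, their baseline exists only as a band, and the amendment should say how they will be handled.

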## **Methodology**

### **Study Design**

We used an exploratory sequential mixed method study design to culturally adapt the Smoking and LDCT Questionnaire and address the sociocultural contexts of smoking and LDCT LCS among African Americans. For Objective 1, thirty African American smokers eligible for LDCT LCS completed the qualitative interview/focus group. We integrated qualitative themes from the interview/focus groups were matched to survey domains (Objective 2) and some themes were used to develop a Multiple levels intervention integrating lung cancer screening and smoking cessation (MILS) intervention curriculum for a culturally adapted smoking cessation and LDCT LCS. For Objective 2, we will conduct a randomized control trial (RCT), which is a type of study that compares the effectiveness of different treatments or interventions by randomly dividing participants into groups, with a wait-list control design, which is when the control group serves as the untreated comparison group during the study, but eventually receives the treatment at a later date, to determine the Effectiveness of a Multiple levels intervention integrating lung cancer screening and smoking cessation (MILS) for African Americans undergoing LDCT. For Objective 3, we will conduct 30 qualitative key informant interviews (10 for each level) to identify barriers and facilitators that influence the adherence and implementation of MILS.

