**\*\*Year 1 highlighted in blue**

## Study Methods

### Procedure

**Objective 1:** The research assistant (RA) is in charge of the patient schedule (list provided by the Radiology department and sends the schedule to UMC to reserve the patient room before the interview. The R.A. contacts the patient and confirms he/she will attend the interview. Eligible participants will be approached in the clinic by staff recruiters. The recruiter will briefly explain the study. If the participant is interested, they will meet with a research assistant (RA) in a private room to learn more about the study and will be provided with an information sheet on the details of the study and complete the interview. R.A.s will be trained to recruit, consent and conduct interviews for the proposed study. During the interviews, the project coordinator will follow a semi-structured interview guide with a list of questions to ask participants to share their personal perspectives and experiences about their experience, awareness, intention, and barriers about smoking cessation and LDCT LCS. These in-depth interviews will last about 45 minutes and will be recorded for transcription. These findings will guide Objective 2. If the participant agrees to participate in the study, the research staff will then conduct the interview.

After the interview, the patient will be required to sign two sign in sheets to confirm he/she received the \$100 clinic card.

**Objective 2:** The proposed study will conduct a randomized clinical trial examining the effectiveness of a multiple levels intervention integrating lung cancer screening and smoking cessation (MILS) for African Americans undergoing LDCT. The developed MILS Intervention using the Theory of Planned Behavior and the Transtheoretical Model as a guiding framework, the content of the targeted smoking cessation intervention and LDCT uptake.

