### **Data Analysis**

**Objective 1:** Qualitative data collected from semi-structure interviews, which is a research method that combines a set of predetermined questions with the ability for the interviewer to explore specific themes or responses. These interviews allow for a mix of predetermined questions and others that are not based on the participant's responses. The interviews will be transcribed, de-identified, and enter into Atlas.ti for data analysis. A thematic analysis will be conducted to understand participants' perspectives on smoking cessation and LDCT LCS. The primary analysis will be performed by two researchers independently. These two researchers will review the first 5 interviews to open code the data and to identify emergent themes. The multidisciplinary research team will then have meetings to discuss, operationalize, and refine the codes and themes to develop a coding scheme. The two researchers will use the developed coding scheme to independently code all the transcripts. They will have regular meetings to review coded transcripts together, identify and reconcile any coding discrepancies, and add newly merged codes and themes into the coding scheme. We will calculate the code frequencies to identify the most frequently mentioned points by participants under each theme. The final coding results will be reviewed and shared with all research team members for feedback and revision.

**Objective 2:** We plan to enroll a total of 250 participants (125 for each group; experiment and control group). Assuming a 20% attrition rate, we estimated 200 (100 per group) participants at the end of the study at the 6-month follow-up visit. A significant level of 0.05 is applied. We estimated that the biochemically validated 7-day point-prevalence tobacco abstinence rates at 6 months are 20-30% for the MILS group and 5% for the control group (Martha Andritsou et al., 2016). A sample size of 200 achieves 85.6-99.6% power to detect the group difference in tobacco abstinence rates at 6 months based on the two-sided Fisher's exact test. For the LDCT uptake, we estimate that the LDCT uptake at 6 months is 32-40% for the MILS group and 15% for the control group (Young PC et al., 2020; Coral Olazagasti et al., 2022). A sample size of 200 achieves 76.5-97.2% power to detect the group difference of the LDCT update based on the two-sided Fisher's exact test (Ryan, 2013).

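### LDCT uptake, a powered Objective 2 outcome, rests on questionnaires alone and has no common time window in the two arms; dated scan records counted from randomisation would reduce the resulting bias

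*Protocol*

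**What the plan says.** - **Source of the outcome.** Study Questionnaires/ Assessment Tools: "the LDCT uptake and intent to LCS constructs were measured by previously validated questionnaires". No check against hospital or radiology records is described for Objective 2. The other powered outcome, 7-day abstinence at 6 months, is to be biochemically validated.
- **Timing.** The same section: "Primary outcomes were measured by survey before intervention, immediately after intervention, and 6-month after intervention". Data Analysis gives LDCT uptake at 6 months without saying from when.
- **Control arm.** Study Design: "the control group serves as the untreated comparison group during the study".
- **Entry.** Study Sample/Recruitment recruits at one hospital, the University Medical Center (UMC), and admits people who are eligible for LDCT "or have received a LDCT exam in the past".
- **Sample size.** Data Analysis enrols 250 (125 per arm), assumes 20% attrition, and states: "A sample size of 200 achieves 76.5-97.2% power to detect the group difference of the LDCT update". The assumed rates are 32-40% for MILS and 15% for control, with a two-sided Fisher's exact test at 0.05.
- **Deferral.** Study Questionnaires/ Assessment Tools leaves the Year 2 measurements and all survey instruments to a later amendment.

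**The concern.** A scan is a dated event that normally leaves a record. Taking it from a questionnaire alone, in a trial whose participants know their arm, creates three problems.

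1. **Reporting.** MILS promotes the behaviour that is being self-reported. If MILS participants over-report more than controls, the bias favours MILS.
2. **Missing data.** A survey outcome is unobserved in anyone who does not return, which on the protocol's own assumption is 50 of 250. A later analysis plan can choose an analysis set, but it cannot supply scan dates that were never collected or authorised.
3. **Window.** An untreated control has no intervention end from which to count. Uptake is cumulative, so if MILS participants were asked about a longer period than controls, they would show more scans with no effect at all. Because people with an earlier LDCT can enrol, a question without a start date could also count scans done before randomisation.

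**Working it through.** **Inputs.** From Data Analysis: 125 randomised and 100 retained per arm; uptake 32% or 40% vs 15%; two-sided Fisher's exact test at 0.05. Capture, drop-out uptake, over-reporting and window lengths are assumptions, because the protocol gives none of them.

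**Method.** Power = sum, over all pairs of counts for which the two-sided Fisher p-value is at most 0.05, of Bin(x1; n, p1) × Bin(x2; n, p2).

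**Step 1: the plan's own figure.** At 100 per arm the exact calculation gives 77.2% and 97.4%. The pooled normal approximation with the difference reduced by 1/n gives 76.5% and 97.2%, exactly as stated. The stated power is sound for 200 observed participants.

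**Step 2: all 250 observed, rates unchanged.**

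| MILS vs control | 100 per arm | 125 per arm | Gain (points) |
|---|---|---|---|
| 32% vs 15% | 77.2% | 86.6% | 9.4 |
| 40% vs 15% | 97.4% | 99.3% | 1.9 |

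**Step 3: incomplete capture.** If records find a share s of true scans, equal in both arms, the rates become 0.32s and 0.15s at 125 per arm.

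| s | Power |
|---|---|
| 100% | 86.6% |
| 95% | 84.1% |
| 90% | 81.3% |
| 85% | 78.2% |
| 83% | 76.8% |
| 80% | 74.7% |

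Power falls back to 77.2% between 83% and 85% capture.

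**Step 4: drop-outs unlike completers.** Suppose 32% holds for completers only, and control uptake is 15% throughout. The MILS rate over all 125 is 0.8 × 32% + 0.2 × (drop-out rate).
- Drop-outs at 15%: 25.6% + 3.0% = 28.6%, power 69.7%.
- Drop-outs at 23.5% (halfway): 25.6% + 4.7% = 30.3%, power 79.2%.
- Drop-outs at 32%: power 86.6%, as in step 2.

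**Step 5: over-reporting.** True uptake is 15% in both arms, 100 per arm, and a share f of unscanned MILS participants report a scan. The observed MILS rate is 15% + 85% × f.
- f = 5%: 19.25%, false rejection 9.2%.
- f = 10%: 23.5%, false rejection 27.1%.

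**Step 6: unequal windows.** No true effect, and a constant rate giving 15% in 6 months: h = −ln(0.85)/6 = 0.0271 per month. Uptake by month m is 1 − exp(−h·m). Controls are assessed at 6 months, with 100 per arm.

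| MILS window | MILS uptake | False rejection |
|---|---|---|
| 6 months (equal) | 15.0% | 3.3% |
| 7 months | 17.3% | 5.0% |
| 8 months | 19.5% | 9.9% |
| 9 months | 21.6% | 17.8% |

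The 3.3% in the first row is the true size of this conservative test. A one-month mismatch raises rejection only to the nominal 5%.

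**The case against.** The strongest reply is that most of this is not yet settled. The protocol defers the Year 2 instruments to an amendment, so the wording, dating and look-back of the LDCT item are still to come. That is fair. However, the current text already commits to the questionnaire as the source and to a survey clock that runs from the intervention, and the pending amendment is the natural place to change both.

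Several stronger readings are tempting, and the document does not support them.

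- **That only completers will be analysed.** The 200 is the basis of the power calculation. No analysis set or missing-data rule for uptake is stated, and the analysis plan may settle it.
- **That the windows are unequal.** The length of MILS is not given, and 6 months has no stated origin. Control visits matched to MILS visit dates would fit the text equally well.
- **That the team already has the records.** The "list provided by the Radiology department" in Procedure serves the scheduling of Objective 1 interviews. It does not show record access for the 250 trial participants.
- **That records would remove bias.** Recruitment at UMC does not mean that scans are done there. The study does not itself provide screening, and community health workers connect MILS participants to services, so outside scans could differ by arm. A self-report supplement also brings back some self-report and some missingness.
- **That about 10 points of power are there for the taking.** The gain is about 2 points at the upper end of the protocol's range. It depends on capture and on how drop-outs behave (steps 3 and 4).

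**Conclusion.** The point holds in limited form and should be acted on. As written, a powered outcome is unverified self-report in participants who know their arm, is unobserved in the expected 50 drop-outs, and has no defined window in the control arm. The case for change rests on bias and definition, with power secondary.

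Exact power would rise by 9.4 points (32% vs 15%) or 1.9 points (40% vs 15%), but only if capture is near complete and drop-outs have the same uptake as completers. The low-end gain is gone at about 83% capture, and power falls to 69.7% if MILS drop-outs have 15% uptake. Even then, counting everyone randomised may be preferable on grounds of bias.

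The false-rejection figures for over-reporting and for unequal windows show what could happen under stated assumptions. They do not describe what the protocol prescribes.

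**What to change.** In the Year 2 amendment:

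1. Define LDCT uptake as an LDCT dated after randomisation and within one fixed window, identical in both arms, sought in UMC records for all 250 randomised.
2. Supplement with participant-reported outside scans, confirmed where possible, and report confirmed and unconfirmed scans separately.
3. Keep the questionnaire for screening intention and attitudes.
4. Schedule the post-intervention and 6-month assessments from the randomisation date in both arms.
5. Quote power of 86.6-99.3% only if near-complete capture can be supported. Otherwise show the range under lower capture and lower uptake in drop-outs.

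**Cost.** A records pull and authorisation wording in the Aim 2 consent form, which must be in place before enrolment. Scans outside UMC will still be captured incompletely, and the self-report supplement only partly covers them.
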